A number of human physiological parameters correlate with mood and respond in the presence of stress, such as voice, skin conductance and pupil diameter. Capturing human voice or speech is generally less obtrusive than capturing other stress sensitive physiological signals, which require on-body sensing equipment and might also introduce safety concerns. As we focus on modeling and improving patient-caregiver relationships, we will build on sensing capability in acoustic events for monitoring patient and caregiver moods, stress and their vocal interactions. As the demands of caregiving for a person with ADRD escalate, many families struggle to maintain healthy relationships with each other, which directly leads to intensified stress on family caregivers. The stress on caregivers, in turn, exacerbates the disease and condition of ADRD patients. Therefore, detecting and modeling stress in caregivers, and providing them with just-in-time training and recommendations becomes crucial. It is a notorious difficult challenge to detect stress from voice, but our approach is to apply novel machine learning techniques that combine multi-instance learning and transfer learning. We have shown these techniques work well for detecting anxiety from voice [25], and propose to now apply this to stress detection.

The end-goals of our research are to provide real-time objective behavior monitoring to reduce in-home patient care cost and to improve the quality of interactions between persons with ADRD and their family caregivers. To achieve the goals, only passively recording what happened for posterior analysis and response is insufficient; real-time recommendation becomes necessary and beneficial to both patients and caregivers. For caregivers, this helps them improve their relation with patient, and may provide them with new insights of how their actions and reactions to their loved one with dementia can either calm or escalate a situation. Furthermore, from a system development perspective, patient's and caregiver's responses to the system's output, e.g., monitoring data, recommendations, become an invaluable source of supervision for us and the back-end automated system to further refine the deployed classifiers and control pipelines.

III. Procedures

A. Research Design

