There are two important research questions this study aims to address: 1) how to generate effective and accurate recommendations; and 2) how to adapt the recommendation generation according to patients' and caregivers' feedback. To the best of our knowledge, no existing in-home health monitoring system provides this capability, instead recommendations are developed in an ad-hoc manner and generated ahead of time and independently of the interaction dynamics. Due to the nature of dementia disease and the consideration of patient safety, we will *only study recommendations for caregivers*. But the technical solutions we examined here are general, and can be applied to other health recommendation scenarios. We should note that we are not replacing medical care; study participants (e.g., caregivers) will be provided information to seek help from their regular healthcare provider or emergency services as needed.

The proposed collaborative research will take place over four years and will follow the outlined timeline:

Year One: In the first year, focus will be on building the front-end monitoring architecture. In-suites sensing and monitoring components will be built and customized for collecting the

participants' vocal and psychological signals. Joint acoustic signal analysis and text mining algorithms will be explored. At this stage of single module development, offline dataset will be used for evaluation purpose. A study consultant, will also assist the study team in developing and pilot-testing a checklist to assess for fidelity of the educational training we deliver to caregiver participants.

Year Two: We will be working on system integration and unit test of the intergraded components in the system. In the meanwhile, from the second half of year two, we will start recruiting patients for our system deployment and evaluation purpose. The PI and research assistant will work with the recruitment clinic to consent and enroll the pilot patients, collect study data, and will be on-call to answer caregiver questions as they may arise. We set “5-7 patients enrolled per month” as our recruitment milestone, and thus it takes about 2 months to recruit 8-10 patients for phase 1 pilot study and about 4 months to recruit 25 patients for phase 2 system evaluation.

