Fidelity checks will be performed , and retraining of GRAs will be performed based upon results of fidelity checks. The study team will meet weekly to ensure that recruitment and caregiver trainings are proceeding smoothly and to problem-solve with staff if necessary.

Year Three: According to our evaluation plan, we will start our second phase 4-month pilot evaluation at the beginning of year three (one month for constructing baseline measurement and three months for controlled studies). All personnel will work together to conduct the pilot study and collect feedback from real patients and clinician experts to refine the system design in an iterative way. Fidelity checks will be performed and Re-training of GRAs will be performed by based upon results of fidelity checks.

In particular, we will conduct the patient clinical interviews, and will work with an expert clinical panel to obtain feedback on the system. The caregiver interviews will be analyzed for the specifics of how the recommendation affects the caregiver-care recipient family dynamic. The monitored data, system's automated prediction results will be analyzed, and the system design and implementation revised and updated according to the patients' and clinician experts' feedback. Upon finishing the pilot study, we will start our phase 2 system-level evaluation, which will last 18 months. Note, before we start the phase 2 evaluation, we would have around 2 to 4 months period to adjust to unexpected delays/barriers in algorithm design, system development, or patient recruitment. We will make sure everything is planned and on schedule before we move onto the phase 2 system level evaluation.

Year Four: The second phase of system level evaluation will be undertaken based on the information and lessons learned from phase one. This will include new technical solutions, refined computational models and system deployment designs. All personnel will work together to conduct full system evaluation. We will collaborate with clinicians in the two study sites at Ohio State University Medical Center the in our user study Clinicians, will help us recruit patients for participation and provide feedback on the system development.

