Importance of the Knowledge to Be Gained. There may be immediate benefit to the subjects participating in the study, although we do not guarantee this, as family caregivers will be given specific knowledge and helpful reminders to mitigate potentially problematic behaviors regarding care of their loved one with ADRD. If successful, the knowledge gained will be important because of its substantial potential to enhance the treatment of difficult to manage, prevalent, and burdensome care problems of persons with ADRD, increasing their quality of life, reducing caregiver burden, delaying or reducing institutionalization, and decreasing the costs of caring for persons with AD in the future.

E. Internal Validity

The purpose of this study is primarily to establish feasibility and test the model. If we can establish that our system reduces emotional reactivity and that patient and caregiver self-reported and observed outcomes improve over time compared to an individualized baseline period, we will have established justification for a more comprehensive design that will more fully test this system against a credible alternative.

Thus, the caregivers will fill out the measures provided to them and then their interactions with the patients will be monitored for a month to establish a baseline of functioning. We will assess levels of reactivity during caregiver-patient interactions and the time it takes for them to return to their own baseline. At the end of the one-month assessment period, the caregiver will be brought in for training on the recommendations, after which they will receive recommendations when the system detects emotional reactions when the caregiver and patient are with each other. The recommendations will be personalized over time. Effectiveness of the recommendations will be assessed by examining whether the recommendations reduce the frequency and intensity of the negative patient-caregiver interactions and the time required for reactivity to return to baseline in real time, as assessed by information recorded by the monitoring system. Effectiveness also will be assessed by monitoring change in the self-report measures during the baseline period compared to the period in which the caregiver is receiving the recommendations.

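### III.E reads effectiveness from a monitoring system that the protocol allows to be refined during use, without requiring one scoring version for both periods of a dyad

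*Protocol*

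**What the plan says.** **Outcome and comparator.** Section III.E (Internal Validity) sets out two strands of effectiveness. The first asks whether negative interactions become less frequent and less intense, and whether reactivity settles faster, "in real time, as assessed by information recorded by the monitoring system". The second is change in the self-report measures. Improvement is judged "compared to an individualized baseline period". Section III.A (Research Design) states that the study has one group and no control. Although III.D (Year Three) describes the four-month pilot as "one month for constructing baseline measurement and three months for controlled studies", no concurrent comparator is planned.

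**Refinement of the system.** Section II (Background and Rationale) says that participants' responses to the system's output "become an invaluable source of supervision for us and the back-end automated system to further refine the deployed classifiers and control pipelines". Section III.D (Year Three) says that staff running the pilot will "collect feedback from real patients and clinician experts to refine the system design in an iterative way". For Year Four it announces "new technical solutions, refined computational models and system deployment designs", drawing on phase one.

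**Adaptation of the intervention.** Section III.D opens with the question "how to adapt the recommendation generation according to" participants' feedback, and III.E adds: "The recommendations will be personalized over time". These two statements concern what caregivers are sent, not how interactions are scored.

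**Safeguards.** No section fixes a classifier version for a dyad, requires both of its periods to be scored alike, commits to re-scoring stored recordings, or asks for a log of versions. Section III.D does say that acoustic data go to the partner university for analysis and storage, but not in what form they are kept.

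**The concern.** For the first strand of effectiveness, the software is the measuring instrument. Baseline always comes first and nobody is observed without the intervention. Anything that changes with time inside a dyad, including the instrument, therefore coincides with the start of the recommendations.

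If the classifier or its threshold changes between a dyad's two periods, some of the apparent change in negative interactions is a change in detection. Within-dyad comparison does not remove it, and no control arm shows it.

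Two things make this worth settling in the protocol. III.E uses improvement over baseline to justify a later, more comprehensive comparative design, so the reading feeds a decision. And the remedy depends on conduct: if re-scorable data and version dates are not kept while the study runs, a later analysis plan cannot recover them.

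**Working it through.** The plan gives no figure to reproduce: no detection accuracy, outcome variance, effect size or test for these outcomes. The check is mainly one of reading the passages together.

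**Step 1. Can scoring change within a dyad?**
- Section II names deployed classifiers as a target of refinement from participants' responses, but sets no timing.
- III.D (Year Three) places iterative refinement alongside the conduct of the pilot, which contains both a baseline month and the three months after it. It speaks of system design and names no classifier update within a dyad.
- III.D (Year Four) dates refined models to the gap between phases. That leaves change within a dyad unbiased.
- An update inside a dyad's participation is therefore permitted, but not declared.

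**Step 2. Which period would an update reach?** A dyad's responses to recommendations exist only once recommendations have started. An update trained on them can affect only the later period, and not its beginning, unless baseline is re-scored. An update from other dyads' data could fall anywhere. Enrolment is staggered (5-7 patients per month, III.D Year Two) and participation lasts up to four months, so a change on one calendar date would meet dyads at different points, some still in baseline.

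**Step 3. What would it do to the outcome?** Take frequency only, with no true change. All values below are assumptions.

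Detected rate = true rate × sensitivity / precision. If the new version scores a fraction k of the three recommendation months, the period ratio is 1 + k × (full ratio − 1).

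| Assumed change in the classifier | Full ratio | k = 1 | k = 2/3 | k = 1/2 | k = 1/3 |
|---|---|---|---|---|---|
| Precision 0.70 to 0.80 | 0.70/0.80 = 0.875 | −12.5% | −8.3% | −6.3% | −4.2% |
| Sensitivity 0.70 to 0.80 | 0.80/0.70 = 1.143 | +14.3% | +9.5% | +7.1% | +4.8% |
| Both | 1.143 × 0.875 = 1.000 | 0% | 0% | 0% | 0% |

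Other assumptions give other sizes. Let the detected share be sensitivity × p + (1 − specificity) × (1 − p), with true negative share p = 0.10, sensitivity 0.80 and specificity 0.90. The detected share is 0.08 + 0.09 = 0.17. Raising specificity to 0.95 gives 0.08 + 0.045 = 0.125, an apparent fall of 26.5% at k = 1. Lowering it to 0.85 gives 0.08 + 0.135 = 0.215, a rise of 26.5%.

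**Step 4. Consequence for a test.** Assume a two-sided 5% paired t-test on the log rate ratio with the target of 30 dyads (III.B), an assumed SD of 0.3 to 0.5, and the precision case above. With no true effect, the rejection rate is:
- 21% to 10% if the change comes at mid-period in every dyad;
- 9% to 6% if it comes at mid-period in half the dyads;
- 65% to 29% if every dyad switches exactly at its own baseline boundary, a pattern that the protocol nowhere describes.

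**Step 5. Effect of the fix.** If one version scores both periods, sensitivity and precision no longer differ because of version. The version-induced ratio is 1 and this source of inflation disappears.

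**The case against.** The strongest reply is that this is an omission rather than an error. The algorithm version that derives an endpoint is often left to an analysis plan or data-processing manual, and III.E as written is compatible with uniform re-scoring of stored data. Several supporting points are fair:
- The sentence in Section II is background text about development aims.
- In III.E, the words about real time follow directly on recovery time and may describe only that. The source named is recorded information, which suits later scoring.
- The dated model changes fall between phases, and much of the planned feedback is aimed at the recommendations.
- The yes/no and star ratings in III.D (Visit 2) are poor labels for training detection.
- Every input to the illustration is assumed, and its most extreme case is implausible. Shifts in opposite directions across dyads could cancel.

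All of this limits the point without removing it. The protocol itself ties the outcome to the monitoring system and itself foresees refining deployed classifiers. The data needed for a repair must be kept during conduct, which an analysis plan written later cannot secure.

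A reader might infer more: that classifiers will be retrained within dyads, that effectiveness will certainly be scored from live output, or that the result will be biased towards benefit. The documents support none of these. No within-dyad update is announced, re-scoring is not excluded, and the shift could run in either direction or be nil.

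**Conclusion.** The point holds as a conditional one. III.E permits a dyad's two periods to be scored by different classifier versions, and with no control group any such difference would be inseparable from the intervention effect on the monitoring-derived outcomes. Whether it will happen, in which direction and by how much cannot be derived from the protocol. The percentages above show only how the result depends on assumed accuracy and timing, and should not be read as a forecast.

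Severity is low to moderate. The self-report strand is untouched, the study is primarily about feasibility, and success leads to a further test rather than to a claim of efficacy. It should still be fixed because the remedy is cheap and the loss may be irreparable if re-scorable data are not kept. Confidence is moderate, since the case rests on what the text allows rather than on what it schedules.

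**What to change.** Add to III.E:
- The live system may adapt for the purpose of triggering texts.
- For each dyad, the monitoring-derived effectiveness outcomes are scored by one fixed classifier version and one threshold, applied to the stored acoustic data or features of both the baseline and the recommendation period.
- Re-scorable audio or features are retained, with a log of classifier versions and the dates on which they were in use.
- Counts from the live system are reported as operational data only.

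The fixed version may be personalised, in keeping with the project's aim of tailored classifiers, provided that the same version scores both periods. Keeping a dyad's own data out of training is an optional extra, not a condition.

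The cost is a few sentences, batch re-scoring, a version log, and storage in re-scorable form. Storage carries some privacy cost, greater for raw audio than for features. The fixed version may be slightly less accurate than the latest one. There is no added burden on participants and no change to the intervention.

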The research design used in this project is a single-group, longitudinal design. All study participants will receive the interventions. Therefore, randomization is not occurring in this project and there is no control group.

This project focuses on building a behavior monitoring and recommendation system for in-home dementia patient care. In the front-end, a flexible sensing and communication platform will support the proposed monitoring, analytics, and recommendation tasks. In the back-end, we focus on multi-modal behavior monitoring with a special emphasis on patient and caregiver vocal events, and the behavior dynamics between them. In particular we focus on detecting mood and stress in a personalized and real-time manner.

To conquer sparsity issue in statistical model training and enable rapid deployment of analytical models, we will develop solutions based on transfer learning [22, 23, 6], such that the labeled instances and learned models can be shared across patients and monitoring scenarios. This further facilitates scalable deployment of our proposed in-home monitoring system.

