To fully address these project goals, we will provide caregivers with brief, face-to-face or virtual training on the recommendations that our system will generate for them. These training sessions will take place in-person—in their own home or at the Ohio State University depending on which setting is easiest for them—or via telephone or Zoom call. They will be trained by a graduate research assistant (GRA) who will be supervised by [name] (via Skype) and [name] (on site). Recommendations will be personalized to include the caregiver's preferred name (e.g., Jane or [name]), as this is found to enhance the efficacy [1]. Although we describe a proposed outline of the training in more detail below, we will engage in a one-month data gathering and baseline assessment phase before we implement this training with caregivers. Information that we gather will be used to refine and better target the training described here before implementation. For example, if we learn that most difficult interactions occur during the dinner hour, we might adapt the training to more specifically focus on behaviors around feeding or eating. Based on the literature regarding problematic caregiver-patient interactions, four types of recommendations will initially be generated when the system indicates that the caregiver-patient might be experiencing high levels of arousal in proximity with each other.

Before we send one of the specific recommendations, we will text the caregiver to insure that the care recipient is safe and is not experiencing acute medical changes. In this text, we will recommend that the caregiver contact the primary care physician (if not urgent) or dialing 911 (if urgent).

The **first** category of reminders would be to take a brief time-out from the interaction, which also has been demonstrated in multiple studies on dyadic interactions to be effective in ameliorating problematic exchanges and reducing emotional reactivity [9, 5, 34]. We will use the time-out method described in [9] and the caregiver will again be given training from GRA in this technique.

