The **fourth** category of reminders are strategies that problem solve on how to manage the patients if they are agitated, restless, or are disengaged, which are based on recommendations to modify the environment provided by the “Savvy Caregiver” program. This program is a product of our study consultant, [name] [12, 13], and based upon addressing unmet needs and a lowered stress threshold in persons with ADRD. At the first study visit, caregivers will be provided with information regarding the need to address potentially unmet basic care the recipient needs, such as toileting and hunger, and will be asked to identify 3-4 pleasant activities they could engage their loved one with ADRD in if they become agitated, restless, or disengaged. Examples of this include taking a walk, looking at photo albums together, gardening, listening to pleasurable music together, etc. These activities are individualized, based on the interests of the individual persons with ADRD. Caregivers would receive a text recommendation to identify unmet needs or to engage their loved one in one of their pre-identified pleasurable activities to decrease agitation, stress, and to improve mood. Individualized, social activities are found to be efficacious and cost-effective in redirecting a person with ADRD and to decreasing disruptive behaviors [33,11,15]. Caregivers will receive a handouts on all of these five strategies.

B. Sample

The study sample will be drawn from eligible patients receiving treatment either at the Center for Cognitive and Memory Disorders clinic at Ohio State University or at community-based settings. For recruitment from community-based settings, the Center for Clinical and Translational Science (CCTS) will upload a paid advertisement for this study on Facebook and/or Instagram, a social media platform. The advertisement will lead potential participants to the Caregiver Research Study website (<https://studysearch.osumc.edu/studies/2837/>) and provide detailed information of this research. CCTS will be also affiliated with other organizations and State agencies providing caregiving or ADRD resources; the uploaded post on CCTS Facebook and/or Instagram will be shared with the organizations. The duration of the first social media

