Visit 1: The study information brochure and the study consent forms will be reviewed in person, via video call, or via telephone with the potential study participants. Written, informed consent will be obtained for both the family caregiver and the persons with dementia. If informed consent is unable to be obtained for the person with dementia based upon their scores on the Capacity to Consent instrument, their surrogate decision-maker will provide informed consent and assent for the person with dementia will be ascertained by the study team member. If willing, participants will be asked to sign for consent electronically using a REDCap link sent via email. In REDCap participants will provide electronic signatures on the consent form indicating they agree to participate in this study. Following the consenting procedure, the acoustic monitor (microphone) and accompanying laptop computer (for transferring the acoustic data to the Cloud for translation processes to occur) will be placed in the participant's home at the location that is amenable to the study participants. We anticipate this will be the kitchen/dining area and the living room areas of the home as many interactions occur in these locations. No acoustic monitoring will occur in any areas of the house that they do not wish to have a microphone placed. A 5-minute audio

recording will be obtained from the caregiver and person with dementia. The recording will be uploaded to the recommender system to generate a person ID for vocal recognition during the study.

The acoustic monitoring will occur for up to 1 month to establish baseline interactions between the family caregiver and the persons with dementia. A Smart Phone will be given to the caregiver for use during the study period for the purpose of receiving recommendations and providing feedback through daily and weekly online surveys. Written and verbal instructions on the use of the acoustic monitoring and the Smart Phone will be provided to study participants. There are no steps that participants need to follow to maintain the equipment, other than keeping the microphone and laptop plugged in to an electric outlet and recharging the Smart Phone. We will also ensure the internet connection via Wifi is enabled.

The following surveys will be administered via paper and pencil forms or RedCap to the family caregiver:

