2. TICS

During Visit 1, research personnel will prompt the family caregiver to establish an emergency plan. This plan is meant to reinforce use of previously established procedures or create procedures to be used in the event of an emergency. Research personnel will stress that the study equipment is not monitored and is not capable of contacting emergency services and should not be used for such activity. Examples of an emergency plan could include, but are not limited to, notifying a healthcare provider, calling 911, or calling another family member. Caregivers will be reminded periodically to follow the procedures of their emergency plan in the event of any emergency.

We anticipate Visit 1 will take between 90-135 minutes.

Between visits 1 and 2, participants will complete a short survey about their experience deploying the study equipment in their home. The questionnaire will take about five to ten minutes to complete.

Visit 2: Upon completion of the first two weeks to one month of baseline data collection, the trained Graduate Research Assistant will visit the study participants in their homes or set up a

virtual meeting via Zoom or telephone to educate the participants regarding the text messages they will be receiving from the study team when stressful situations are identified. The Graduate Research Assistant will also train caregivers on how to perform mindfulness-based activities. A standardized training guide will be used for all participants by the trained GRAs. During the visit, a principal investigator (PI) may monitor whether the stress management education is delivered as intended (i.e., intervention fidelity check) with no recordings. Retraining of GRAs may be performed based upon the results of fidelity checks. Caregivers will be asked to select personal preferences for messages and helpful reminders they will receive in the text messages that would prompt their understanding of the text messages received from a pre-set list of choices. Additionally, family caregivers will be taught to respond to the daily and weekly feedback surveys regarding their use of the text messages.

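### Fourth-category caregiver content is timed at Visit 1, when the acoustic baseline starts, although training is otherwise placed after baseline

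*Protocol*

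**What the plan says.** A. Research Design lists four categories of recommendation. For the fourth, which concerns modifying the environment, it says: "At the first study visit, caregivers will be provided with information regarding the need to address potentially unmet basic care the recipient needs". In the same sentence caregivers "will be asked to identify 3-4 pleasant activities they could engage their loved one with ADRD in if they become agitated". Texts sent later in the study then draw on those choices.

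Earlier in the same section the order is different: "we will engage in a one-month data gathering and baseline assessment phase before we implement this training with caregivers". E. Internal Validity repeats that order, with training at the end of the one-month assessment. Under Study Visits, the training visit is Visit 2, held "Upon completion of the first two weeks to one month of baseline data collection".

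The Visit 1 description starts the recording: "The acoustic monitoring will occur for up to 1 month to establish baseline interactions between the family caregiver and the persons with dementia". On the comparator, A. Research Design says that "randomization is not occurring in this project and there is no control group".

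**The concern.** The study judges effectiveness against each dyad's own baseline period. For the outcomes taken from the monitoring system (how often negative interactions occur, how intense they are, and how long reactivity takes to settle), that baseline is the acoustic recording that begins at Visit 1. With no control group, nothing else is available to compare against.

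The baseline should therefore be free of intervention content. If caregivers are told at Visit 1 to look for unmet needs, and have already named activities to use when the person is agitated, they can act on this the same day without waiting for a text. The recording would then no longer describe usual care alone.

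**Working it through.** The plan gives no figure to reproduce on this point. The check sets the passages side by side.

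1. **Which visit is meant.** Potential Risks to Human Subjects puts the emergency plan at the first study visit. The Visit 1 description puts the same task there: "During Visit 1, research personnel will prompt the family caregiver to establish an emergency plan". B. Sample also calls the consent visit the first visit, and written consent is taken at Visit 1. The first study visit is therefore Visit 1.

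2. **When the acoustic baseline runs.** The microphone is placed at Visit 1 after consent, and baseline recording continues until Visit 2. The Visit 2 description gives two weeks to one month, which is 14 to about 30 days.

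3. **When training is given.** A. Research Design and E. Internal Validity both place it after the baseline, and Study Visits places it at Visit 2.

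4. **Whether the fourth-category content counts as training.** E. Internal Validity names environmental modification, together with mindfulness, as the caregiver training that the fidelity checklist will cover. The Visit 2 description is where a fidelity check on delivery is mentioned. Read together, these imply that environmental-modification training is given at Visit 2. This is an inference, since neither place says so outright.

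5. **Whether a visit description settles it.**
   - Visit 1 covers consent, equipment, a voice recording, surveys and the emergency plan.
   - Visit 2 covers the text messages, mindfulness, and a choice of message preferences from a fixed list. That choice is not clearly the same step, because the fourth-category activities are tailored to the person with dementia.
   - Visit 3 reinforces phone use, replying to texts and mindfulness.
   - Visit 4 collects end-of-study data.
   - None of the four names the unmet-needs information or the choice of activities.

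6. **Which outcomes could be touched.** The caregiver surveys are completed at Visit 1, and E. Internal Validity has them filled in before the month of monitoring. Behaviour adopted at home afterwards cannot be in those scores. Only the acoustic baseline is exposed.

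7. **Direction.** As an illustration only, let T be the true acoustic change from usual care to the full programme, and f the share of T already present during baseline. The observed contrast is T − fT = (1 − f)T. If the content is given after baseline, f = 0 and the contrast is T. If it is given at Visit 1, f depends on uptake and effect, and the protocol states neither. In principle f could lie anywhere from 0 to 1, so no size can be given.

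The scope is therefore one of four categories, its information and activity choice only, over a window of 14 to about 30 days.

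**The case against.** The best defence is that the Visit 1 timing is a stray phrase. It sits in text that the protocol calls a proposed outline. The other sections agree on baseline first, and step 4 above points to Visit 2 for this training. That much stands: the fourth-category sentence is the outlier, and it would be wrong to say that the rest of the document is silent on timing. But it is the only text that attaches this content explicitly to a visit, and staff who followed it would deliver the content before the baseline.

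A second defence is that naming enjoyable activities only gathers material for later texts and is not training. This is fair for the activity choice. It is weaker for the unmet-needs information, which tells caregivers what to look for and can be used at once.

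A third is that the study is mainly about feasibility and that any bias would make the benefit look smaller. Both are true. They lower the stakes, but they do not remove a contradiction about what is delivered before the comparator is measured.

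A reader might also go further and infer that Visit 1 delivery defeats the stated purpose of the baseline: "Information that we gather will be used to refine and better target the training described here before implementation". That would require the refinement to be made dyad by dyad, which the protocol does not say. Its example about the dinner hour fits refinement across the study equally well, and the standardized training guide for all participants fits that reading better.

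**Conclusion.** The contradiction is real and should be settled. If the fourth-category text is followed, the acoustic baseline may already include part of one of the four intervention categories. The acoustic before/after contrast would then be understated, provided that caregivers act on the content without prompts and that it works. The protocol supports no estimate of the amount.

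A reader might infer that the measured effect of the whole programme is diluted. The document does not support that. The self-report baseline is collected at Visit 1 and is not shown to be affected, and the triggered texts begin only after Visit 2 on any reading. Nor is early information clearly a dilution if the question is the narrower one of what the triggered texts add.

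**What to change.** Reconcile the fourth-category text in A. Research Design with the rest of that section, the Visit 2 description and E. Internal Validity. The visit descriptions should state once when the unmet-needs information and the activity choice are given relative to baseline monitoring, consistent with the baseline-before-training design that the protocol sets out. It would help to say there whether the Visit 2 choice of message preferences is the same step.

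If any dyads received the content at Visit 1, the report should say so and interpret their acoustic baseline as including it.

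The cost is wording in the protocol and the training guide. No new visit, measure or analysis is needed.
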